10.3.3 Recording and follow-up of adverse events and/or serious adverse events

AE and SAE Recording

- When an AE/SAE occurs, it is the responsibility of the Investigator to review all documentation (eg, hospital progress notes, laboratory reports, and diagnostics reports) related to the event.
- The Investigator will then record all relevant AE/SAE information in the eCRF.
- It is **not** acceptable for the Investigator to send photocopies of the participant's medical records to UCB in lieu of completion of the UCB AE/SAE eCRF page.
- There may be instances when copies of medical records for certain cases are requested by UCB. In this case, all participant identifiers, with the exception of the participant number, will be redacted on the copies of the medical records before submission to UCB.
- The Investigator will attempt to establish a diagnosis of the event based on signs, symptoms, and/or other clinical information. Whenever possible, the diagnosis (not the individual signs/symptoms) will be documented as the AE/SAE.

Assessment of Intensity

The Investigator will make an assessment of intensity for each AE and SAE reported during the study and assign it to 1 of the following categories:

- **Mild:** An event that is easily tolerated by the participant, causing minimal discomfort and not interfering with everyday activities.
- **Moderate:** An event that causes sufficient discomfort and interferes with normal everyday activities.
- **Severe:** An event that prevents normal everyday activities. An AE that is assessed as severe should not be confused with an SAE. Severe is a category utilized for rating the intensity of an event; and both AEs and SAEs can be assessed as severe.
- An event is defined as 'serious' when it meets at least 1 of the predefined outcomes as described in the definition of an SAE, NOT when it is rated as severe (eg, a severe AE may be either serious or not serious, depending on whether these criteria are also met).

The National Cancer Institute Common Terminology Criteria for Adverse Events should be used as a supportive standardization instrument to evaluate AEs and SAEs but the final intensity grading by the Investigator must be mild, moderate, or severe.

Assessment of Causality

- The Investigator is obligated to assess the relationship between study medication and each occurrence of each AE/SAE.
- A "reasonable possibility" of a relationship conveys that there are facts, evidence, and/or arguments to suggest a causal relationship, rather than a relationship cannot be ruled out.
- The Investigator will use clinical judgment to determine the relationship.
- Alternative causes, such as underlying disease(s), concomitant therapy, and other risk factors, as well as the temporal relationship of the event to study medication administration will be considered and investigated.
- The Investigator will also consult the IB in his/her assessment.
- For each AE/SAE, the Investigator **must** document in the medical notes that he/she has reviewed the AE/SAE and has provided an assessment of causality.
- There may be situations in which an SAE has occurred and the Investigator has minimal information to include in the initial report to UCB. However, **it is very important that the Investigator always make an assessment of causality for every event before the initial transmission of the SAE data to UCB.**
- The Investigator may change his/her opinion of causality in light of follow-up information and send a SAE follow-up report with the updated causality assessment.
- The causality assessment is one of the criteria used when determining regulatory reporting requirements.

Follow-up of AEs and SAEs

- The Investigator is obligated to perform or arrange for the conduct of supplemental measurements and/or evaluations as medically indicated or as requested by UCB to elucidate the nature and/or causality of the AE or SAE as fully as possible. This may include additional laboratory tests or investigations, histopathological examinations, or consultation with other health care professionals.
- An AE should be followed until it has resolved, has a stable sequelae, the Investigator determines that it is no longer clinically significant, or the participant is lost to follow-up. This follow-up requirement applies to AEs, SAEs, and AESIs.
- If a participant dies during participation in the study or during a recognized follow-up period, the Investigator will provide UCB with a copy of any post-mortem findings including histopathology.
- New or updated information will be recorded in the originally completed eCRF.
- The Investigator will submit any updated SAE data to the Sponsor within 24 hours of receipt of the information.

10.3.4 Reporting of serious adverse events

SAE Reporting to UCB via an Electronic Data Collection Tool

- The primary mechanism for reporting an SAE to UCB will be the electronic data collection tool.
- If the electronic system is unavailable for more than 24 hours, then the site will use the paper SAE data collection tool (see next section).
- The site will enter the SAE data into the electronic system as soon as they become available.
- After the study is completed at a given site, the electronic data collection tool will be taken off-line to prevent the entry of new data or changes to existing data.
- If a site receives a report of a new SAE from a study participant or receives updated data on a previously reported SAE after the electronic data collection tool has been taken off-line, then the site can report this information on a paper SAE form (see next section).

Contacts for SAE reporting can be found in [SERIOUS ADVERSE EVENT REPORTING](#).

SAE Reporting to UCB via Paper CRF

- Facsimile transmission of the SAE paper CRF is the preferred method to transmit this information to UCB, see [SERIOUS ADVERSE EVENT REPORTING](#).
- In rare circumstances and in the absence of facsimile equipment, notification by telephone is acceptable with a copy of the SAE data collection tool sent by overnight mail or courier service.
- Initial notification via telephone does not replace the need for the Investigator to complete and sign the SAE CRF pages within the designated reporting time frames.
- Contacts for SAE reporting can be found in [SERIOUS ADVERSE EVENT REPORTING](#).

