8.3.1 Time period and frequency for collecting AE and SAE information

All SAEs will be collected from the signing of the ICF until EOS Visit at the time points specified in the Schedule of Activities (Section 1.3).

All AEs will be collected from the signing of the ICF until EOS Visit at the time points specified in the Schedule of Activities (Section 1.3).

All SAEs will be recorded and reported to the Sponsor or designee within 24 hours, as indicated in Appendix 3 (Section 10.3). The Investigator will submit any updated SAE data to the Sponsor within 24 hours of it being available.

The Investigator is specifically requested to collect and report to UCB (or its representative) any SAEs (even if the Investigator is certain that they are in no way associated with the study medication), up until the End of Study Visit for each participant, and to also inform participants of the need to inform the Investigator of any SAE within this period. Serious AEs that the Investigator thinks may be associated with the study medication must be reported to UCB regardless of the time between the event and the end of the study.

The method of recording, evaluating, and assessing causality of AE and SAE and the procedures for completing and transmitting SAE reports are provided in Appendix 3 (Section 10.3).

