8.3.4 Regulatory reporting requirements for serious adverse events

Prompt notification (24 hours) by the Investigator to the Sponsor of a SAE is essential so that legal obligations and ethical responsibilities towards the safety of participants and the safety of a study treatment under clinical investigation are met.

The Sponsor has a legal responsibility to notify both the local regulatory authority and other regulatory agencies about the safety of a study treatment under clinical investigation. The Sponsor will comply with country-specific regulatory requirements relating to safety reporting to the regulatory authority, Institutional Review Boards (IRB)/Independent Ethics Committees (IEC), and Investigators.

Investigator safety reports must be prepared for suspected unexpected serious adverse reactions according to local regulatory requirements and Sponsor policy and forwarded to Investigators as necessary.

An Investigator who receives an Investigator safety report describing an SAE or other specific safety information (eg, summary or listing of SAEs) from the Sponsor will review and then file it along with the IB and will notify the IRB/IEC, if appropriate according to local requirements.

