8.3.7 Adverse events of special monitoring

For rozanolixizumab, AESMs that require immediate reporting (within 24 hours regardless of seriousness) to UCB are:

- Severe headache
- Severe GI disturbances (ie, abdominal pain, diarrhea, vomiting)
- Opportunistic infection

In case of severe headache or serious headache (regardless of severity), the headache questionnaire (Appendix 21 [Section 10.21]) must be completed. Additional procedures for management of headaches are provided in Appendix 20 (Section 10.20.1).

Procedures for the management of diarrhea, and infections and hypogammaglobulinemia are provided in Appendix 20 (Section 10.20.2 and Section 10.20.3, respectively).

Although hypersensitivity reactions including infused-related reactions and anaphylaxis are not classified as AESM, these AEs will be monitored by the Investigators. If such an event is suspected, it should be managed according the guidance provided in Appendix 20 (Section 10.20.4). In case of suspected anaphylaxis, the Sampson's Criteria Questionnaire (Sampson et al, 2006) in Appendix 22 (Section 10.22) should be completed.

All AESMs will follow the SAE recording and reporting procedures as indicated in Appendix 3 (Section 10.3).

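### The paper back-up for SAE reporting applies only after more than 24 hours of electronic downtime, so a site following it can miss the protocol's 24-hour reporting deadline

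*Protocol*

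**What the plan says.** **Deadline.** Protocol Section 8.3.1 states "All SAEs will be recorded and reported to the Sponsor or designee within 24 hours" and refers to Appendix 3 for the procedure. Section 8.3.4 repeats the limit: "Prompt notification (24 hours) by the Investigator to the Sponsor of a SAE is essential". Section 8.3.7 extends it to AESMs, with the words "AESMs that require immediate reporting (within 24 hours regardless of seriousness) to UCB are" ahead of its list, and sends AESMs through the same Appendix 3 procedures. Section 10.3.3 sets the same limit for follow-up information: "The Investigator will submit any updated SAE data to the Sponsor within 24 hours of receipt of the information".

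**Route.** Section 10.3.4 states "The primary mechanism for reporting an SAE to UCB will be the electronic data collection tool". For an outage it states "If the electronic system is unavailable for more than 24 hours, then the site will use the paper SAE data collection tool". Under the heading for paper reporting, fax is the preferred means of sending the form. Telephone is a narrow exception: "In rare circumstances and in the absence of facsimile equipment, notification by telephone is acceptable". A telephone call does not release the investigator from completing and signing the SAE pages on time.

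**Not stated.** Section 10.3.4 does not say when its 24 hours of downtime begin. Sections 8.3.1 and 8.3.4 do not say when the reporting clock begins.

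**The concern.** Appendix 3 is the procedure that the 24-hour rules rely on. Its back-up for an outage has a waiting time longer than the window it is meant to protect. If the outage begins once the site already holds an unreported event, the two instructions cannot both be met by the stated routes. If the outage is shorter than the trigger, the paper route is never reached at all.

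Safety is the primary objective of this study, and Section 8.3.4 ties prompt notification to the sponsor's legal and ethical duties. A site should not have to choose which reporting instruction to break.

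**Working it through.** The plan gives no figure to reproduce. The check is timing arithmetic.

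**Inputs**
- Reporting limit: 24 hours (Sections 8.3.1, 8.3.4, 8.3.7).
- Start of that limit: assumed to be the site's awareness of the event, called hour 0. The deadline is then hour 24.
- Paper trigger: downtime of more than 24 hours (Section 10.3.4).
- Outage start *u* (hours after awareness, negative if before) and length *L*: not in the documents, so the values below are illustrative. The event has not been entered when the outage begins.

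**Reading A: downtime counted from the true system failure**
- If *L* ≤ 24, the first stated route is the restored system, at hour *u* + *L*. Lateness = *u* + *L* − 24.
- If *L* > 24, the first stated route is paper, just after hour *u* + 24. Lateness is just over *u*.

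| Outage start *u* | *L* = 20 | *L* = 24 | *L* = 36 |
|---|---|---|---|
| +12 | 8 h late | 12 h late | just over 12 h late |
| +10 | 6 h late | 10 h late | just over 10 h late |
| +6 | 2 h late | 6 h late | just over 6 h late |
| +1 | 3 h in hand | 1 h late | just over 1 h late |
| 0 | 4 h in hand | at the limit | just late |
| −1 | 5 h in hand | 1 h in hand | just under 1 h in hand |
| −6 | 10 h in hand | 6 h in hand | just under 6 h in hand |
| −12 | 16 h in hand | 12 h in hand | just under 12 h in hand |

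The report is late whenever *u* ≥ 0 and *u* + *L* > 24. When *u* is negative there is no miss: either the system returns before hour 24 or paper opens before it.

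Example with a short outage: *u* = 10, *L* = 20. The system returns at hour 10 + 20 = 30, paper has never opened, and the report is 30 − 24 = 6 hours late.

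**Reading B: downtime counted from the site's first failed attempt, *d* hours after awareness**

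Paper opens just after hour *d* + 24. For *d* = 0, 1, 6 and 12 that is after hours 24, 25, 30 and 36, or more than 0, 1, 6 and 12 hours past the deadline. The report is on time only if the system returns by hour 24.

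**The two readings on one event**

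Take an outage that starts 12 hours before awareness and lasts 72 hours, with a first attempt 6 hours after awareness. Under A, paper opens just after hour −12 + 24 = 12, with just under 12 hours in hand. Under B, it opens just after hour 6 + 24 = 30, more than 6 hours late. Only the undefined start of the count differs.

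**The case against.** Five arguments can be made against the point.

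1. *The text counts system downtime, not the time since a site noticed.* This stands, and it makes the miss conditional. It helps a site only if the site can find out when the system failed, and Section 10.3.4 does not say how.
2. *The sentence says when paper is required and does not forbid it earlier, while the 24-hour duty continues throughout.* This stands in part. A sensible site may send paper early, but it would be supplying a step that the procedure does not give. Section 8 insists on adherence and rules out waivers.
3. *The site can telephone.* Telephone is limited to rare circumstances without fax equipment and does not replace timely signed pages. A site with a working fax gains nothing from it.
4. *The separate SAE reporting page may cover outages.* That page is not in the review copy, and the amendment history shows that it has carried reporting instructions, so this cannot be excluded. Anything there would still have to agree with Section 10.3.4.
5. *The clinical effect is small.* This stands. A reader might infer that late forms would delay decisions on study drug or IDMC review. The documents do not support that. Section 8 requires immediate safety concerns to be raised with the sponsor or medical monitor at once, and Section 9.7.2 has the IDMC work from periodic reviews.

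**Conclusion.** The instructions conflict, and a site that follows Section 10.3.4 can be late. Two situations produce this: an outage that starts at or after awareness, before entry, and lasts past the deadline; or a count that starts at the first failed attempt, with the system still down at the deadline. In the first situation the delay is *u* + *L* − 24 hours for an outage of up to 24 hours and just over *u* hours for a longer one.

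A reader might infer that every event caught in an outage is late, with reports arriving 24 to 48 hours after awareness. The text does not support this. On the downtime reading, an outage already running before awareness leaves time to use paper. The 24-to-48-hour range needs the outage to start within the 24 hours after awareness, or the count to start at the failed attempt, and the system to stay down until paper opens.

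The conclusion assumes that the reporting clock starts at awareness and that the unseen reporting page adds no outage route. The documents give no outage frequency or duration, so the number of affected reports cannot be estimated. No endpoint, analysis set or statistical analysis is affected. This is an operational safety-reporting correction, worth making because it is cheap and the conflict is in the text.

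**What to change.** In Section 10.3.4, replace the outage sentence with:

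> *If the electronic system is unavailable when an event has to be reported, the site will send the paper SAE form in time to meet the 24-hour deadline from awareness, and will enter the data electronically once the system is restored.*

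Align any outage instruction on the separate SAE reporting page with this wording. AESMs are covered through the cross-reference in Section 8.3.7.

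The change removes the downtime count, so its start no longer needs defining. It touches no dose, clinical rule or analysis. The cost is a few paper forms that duplicate later electronic entries and have to be reconciled.

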10.4 Appendix 4: Contraceptive guidance and collection of pregnancy information

10.4.1 Definitions

10.4.1.1 Woman of childbearing potential

A woman is considered fertile following menarche and until becoming postmenopausal unless permanently sterile (see below).

Women in the following categories **are not considered WOCBP**:

1. Premenarchal
2. Premenopausal female with 1 of the following:
 - Documented hysterectomy
 - Documented bilateral salpingectomy
 - Documented bilateral oophorectomy

Note: Documentation can come from the site personnel's review of the participant's medical records, medical examination, or medical history interview.

3. Postmenopausal female
 - A postmenopausal state is defined as no menses for 12 months without an alternative medical cause. A high follicle stimulating hormone (FSH) level in the postmenopausal range may be used to confirm a postmenopausal state in women not using hormonal contraception or hormonal replacement therapy (HRT). However, in the absence of 12 months of amenorrhea, a single FSH measurement is insufficient.
 - Females on HRT and whose menopausal status is in doubt will be required to use one of the nonestrogen hormonal highly effective contraception methods if they wish to continue their HRT during the study. Otherwise, they must discontinue HRT to allow confirmation of postmenopausal status before study enrollment.

10.4.2 Contraception guidance

Male participants

Male participants with female partners of childbearing potential are eligible to participate if they agree to ONE of the following Treatment Period and for at least 90 days after the final dose of study treatment:

- Are abstinent from penile-vaginal intercourse as their usual and preferred lifestyle (abstinent on a long term and persistent basis) and agree to remain abstinent.
- Agree to use a male condom plus partner use of a contraceptive method with a failure rate of <1% per year as described in [Table 10-1](#) when having penile-vaginal intercourse with a WOCBP who is not currently pregnant.
- Agree to use a male condom when having penile-vaginal intercourse with a woman of childbearing potential who is not currently pregnant.

In addition, male participants must refrain from donating sperm for the duration of the study and for at least 90 days after the last dose of study medication.

Male participants with a pregnant or breastfeeding partner must agree to remain abstinent from penile-vaginal intercourse or use a male condom during each episode of penile penetration for at least 90 days after the last dose of study medication.

Female participants

Female participants of childbearing potential are eligible to participate if they agree to use a highly effective method of contraception consistently and correctly as described in [Table 10-1](#).

Table 10-1: Highly Effective Contraceptive Methods^a

Highly Effective Contraceptive Methods That Are User Dependent^b Failure rate of <1% per year when used consistently and correctly.

Combined (estrogen- and progestogen-containing) hormonal contraception associated with inhibition of ovulation^c
 
 • Oral • Intravaginal • Transdermal

Progestogen-only hormonal contraception associated with inhibition of ovulation
 
 • Oral • Injectable

Highly Effective Methods That Are User Independent^b

Implantable progestogen only hormonal contraception associated with inhibition of ovulation
 
 • Intrauterine device • Intrauterine hormone-releasing system • Bilateral tubal occlusion

Vasectomized partner
 
A vasectomized partner is a highly effective contraception method provided that the partner is the sole male sexual partner of the woman of childbearing potential and the absence of sperm has been confirmed. If not, an additional highly effective method of contraception should be used.

Sexual abstinence
 
Sexual abstinence is considered a highly effective method only if defined as refraining from heterosexual intercourse during the entire period of risk associated with the study medication. The reliability of sexual abstinence needs to be evaluated in relation to the duration of the study and the preferred and usual lifestyle of the participant.

^a In case of newly started contraception pills/IUDs, PI should consider the correct timing of starting/applying such methods in relation to the menstrual cycle and the manufacturing instruction as when these newly started methods would become effective.

^b Typical use failure rates may differ from those when used consistently and correctly. Use should be consistent with local regulations regarding the use of contraceptive methods for participants participating in clinical studies.

^c Hormonal contraception may be susceptible to interaction with the study medication, which may reduce the efficacy of the contraceptive method. In this case, two highly effective methods of contraception should be utilized during the treatment period and for at least 90 days after the last dose of study medication. Pregnancy testing

- A WOCBP should only be included after a confirmed menstrual period and a negative highly sensitive urine pregnancy test.
- Additional pregnancy testing should be performed during the Treatment Period (Section 1.3), at the EOS visit, corresponding to protocol-defined time frame in Section 10.4 after the last dose of study medication and as required locally.
- Pregnancy testing will be performed whenever a menstrual cycle is missed or when pregnancy is otherwise suspected.
- Pregnancy testing, with a sensitivity of ≥ 25 mIU/mL will be performed. Urine pregnancy tests will be performed at all other visits.

10.4.2.1 Male participants with partners who become pregnant

- The Investigator will attempt to collect pregnancy information on any male participant's female partner who becomes pregnant while the male participant is in this study. This applies only to male participants who receive study medication.
- After obtaining the necessary signed informed consent from the pregnant female partner directly, the Investigator will record pregnancy information on the appropriate form and submit it to the Sponsor within 24 hours of learning of the partner's pregnancy. The female partner will also be followed to determine the outcome of the pregnancy. Information on the status of the mother and child will be forwarded to the Sponsor. Generally, the follow-up will be at least 12 months after the delivery date. Any termination of the pregnancy will be reported regardless of fetal status (presence or absence of anomalies) or indication for the procedure.

